5 STUDY ACTIVITIES

5.1 Eligibility Criteria

Subjects must meet all of the following criteria in order to be included in the study. Anything other than a positive response to the questions below will result in exclusion from study participation.

Consent

- ✔ 1. Subjects or their legally authorized representative (if required per local regulations) must understand and personally, voluntarily sign and date an informed consent, approved by an independent ethics committee (IEC)/institutional review board (IRB), prior to the initiation of any screening or study-specific procedures. In Japan, subjects under 20 years of age must voluntarily sign and date an informed consent, in addition to their parent or legal guardian. Legally authorized representation will not apply in the case of Germany and France, and protected persons such as minors, adults under guardianship, pregnant women, persons deprived of their liberty and persons incapable or unable to express their consent cannot be included in the study.

Demographic and Laboratory Assessments

- ✔ 2. Adult male or female, 18 to 65 years of age, inclusive, at Screening.
- ✔ 3. Must not have laboratory values meeting the following criteria within the screening period prior to the first dose of study drug:
 - Serum aspartate transaminase (AST) > 2.0 × upper limit of normal (ULN);
 - Serum alanine transaminase (ALT) > 2.0 × ULN;
 - Estimated glomerular filtration rate (GFR) by simplified 4-variable Modification of Diet in Renal Disease (MDRD) formula < 40 mL/min/1.73 m²;
 - Absolute neutrophil count (ANC) < 1,000/μL;
 - Platelet count < 50,000/μL;
 - Hemoglobin < 9 g/dL.
- ✔ 4. Must not have positive titers for all 3 antiphospholipid antibodies known to be associated with venous thrombotic events at Screening: lupus anticoagulant, anti-beta 2 glycoprotein 1, and anticardiolipin antibody.
- ✔ 5. Are willing and able to comply with procedures required in this protocol.

Disease Activity

- ✔ 6. Clinical diagnosis of SLE at least 24 weeks prior to Screening, meeting at least 4 of the 11 revised Criteria for Classification of SLE according to the 1997 Update of the 1982 ACR OR meeting at least 4 of the 2012 SLICC classification criteria, including at least 1 clinical criterion and 1 immunologic criterion.
- ✔ 7. At Screening, must have at least one of the following:
 - ANA+ (titer ≥ 1:80)
 - anti-dsDNA+
 - anti-Smith+

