Such an event can result from the use of the drug as stipulated in the protocol, as well as from accidental or intentional overdose, drug abuse, or drug withdrawal. Any worsening of a pre-existing condition or illness is considered an AE. Worsening in severity of a reported AE should be reported as a new AE. Laboratory abnormalities and changes in vital signs are considered to be AEs only if they result in discontinuation from the study, necessitate therapeutic medical intervention, meet protocol-specific criteria (see Section 6.2 regarding toxicity management), and/or the investigator considers them to be AEs. Worsening SLE including flares will be captured and analyzed via the disease activity forms (SLEDAI, BILAG, CLASI, and SELENA SLEDAI Flare Index) and will be analyzed as part of efficacy. As such, worsening SLE and flares will not be captured as AEs unless they result in serious outcomes.

The investigators will monitor each subject for clinical and laboratory evidence of AEs on a routine basis throughout the study. All AEs will be followed to a satisfactory conclusion.

An elective surgery/procedure scheduled to occur during a study will not be considered an AE if the surgery/procedure is being performed for a pre-existing condition and the surgery/procedure has been pre-planned prior to study entry. Elective surgery is not permitted during the study until the primary endpoint has been assessed. However, if the pre-existing condition deteriorates unexpectedly during the study (e.g., surgery performed earlier than planned), then the deterioration of the condition for which the elective surgery/procedure is being done will be considered an AE. If the subject undergoes elective surgery, the study drug should be interrupted at least 1 week prior to the planned surgery. If the subject must undergo emergency surgery, the study drug should be interrupted at the time of the surgery. For both elective and emergency surgery, allow reintroduction of study drug once the physician has examined the surgical site and determined that it has healed and there is no sign of infection.

If any of the following events are reported ([Table 3](#)), then the following supplemental report must be completed.

Table 3. Adverse Events Requiring Supplemental Reports

Adverse Events	Supplemental Report

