
Serum Creatinine
	
 • If serum creatinine is > 1.5 × the baseline value and > ULN, repeat the test for serum creatinine (with subject in an euvoletic state) to confirm the results. If the results of the repeat testing still meet this criterion then interrupt study drug and re-start study drug once serum creatinine returns to ≤ 1.5 × baseline value and ≤ ULN. • If confirmed new serum creatinine ≥ 2 mg/dL interrupt study drug, and re-start study drug once serum creatinine returns to normal reference range or its baseline value. 
For the above serum creatinine elevation scenarios, complete supplemental renal eCRF(s).

Laboratory Parameters	Toxicity Management Guidelines
Creatine Phosphokinase (CPK)	
 CPK and aldolase will be measured at every visit but results will be blinded to sites and subjects, as CPK elevation is a known class effect of JAK inhibitors and the results could be unblinding to the sites. If symptomatic myositis is suspected, the site may send a request to the AbbVie TA MD for CPK and/or aldolase results to be unblinded. Request must be approved by the AbbVie TA MD. If confirmed CPK $\geq 4 \times$ ULN accompanied by symptoms suggestive of myositis or rhabdomyolysis, interrupt study drug, complete supplemental CPK eCRF, and contact AbbVie TA MD.
Lymphocyte Count Decreased	
 If confirmed Grade 4 ($< 200/\text{mm}^3$) by repeat testing with new sample, interrupt study drug dosing until lymphocyte count returns to at least Grade 2 (< 800 to $500/\text{mm}^3$) or its baseline value.
White Blood Cell Count Decreased	
 If confirmed Grade 4 ($< 1000/\text{mm}^3$) by repeat testing with new sample, interrupt study drug dosing until white blood cell count returns to at least Grade 2 (< 3000 to $2000/\text{mm}^3$) or its baseline value.
Urine Protein to Creatinine Ratio	
 If > 1 g/day equivalent (1 mg/mg), repeat by testing with new sample, and if confirmed, a renal biopsy will be required. If Class IV lupus nephritis is confirmed, subject must be permanently discontinued from study drug.

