Prothrombin, Partial Thromboplastin		✓														
Lupus Anticoagulant, Anti-Beta 2 Glycoprotein 1, Anticardiolipin Antibody	✓															

	Screening	Baseline	Week 2	Week 4	Week 8	Week 12	Week 16	Week 20	Week 24	Week 28	Week 32	Week 36	Week 40	Week 44	Week 48/ Premature Discontinuation	30-Day Follow Up Phone Call*
Visit Window (Days)			± 3	± 7												
Serum pregnancy test (WOCBP), FSH (non-WOCBP presumed post-menopausal)	✓															
QuantiFERON-TB Gold test (and/or local PPD skin test, T-SPOT.TB Test)	✓															
Clinical chemistry, Hematology (CBC), Urinalysis, Urine Protein to Creatinine ratio (UPCR)	✓	✓	✓	✓	✓	✓	✓	✓	✓	✓	✓	✓	✓	✓	✓	
IgG and IgM	✓	✓		✓					✓						✓	
Blood samples for elsubrutinib and upadacitinib pharmacokinetic (PK) analysis		✓ ^h		✓ ^{h,i}		✓ ^{i,j}		✓ ^{h,i}	✓ ^{h,i}						✓ ^{i,k,l}	
Biomarkers Sample: Whole blood for BTK occupancy analysis (only select # of sites and subjects in the US) ^m		✓ ⁿ				✓ ⁱ			✓ ^h						✓ ^{k,l}	
Biomarker Sample: Whole blood for BTK Y223 phosphorylation assay ^m		✓ ⁿ				✓ ⁱ			✓ ^h						✓ ^{k,l}	
Biomarker Sample: Whole Blood (plasma, serum, DNA and RNA) ^{m,o}		✓ ^j	✓ ^l	✓ ^l		✓ ^l			✓ ^l						✓ ^l	
Biomarker Sample: Whole Blood viable PBMCs ^m		✓ ^j	✓ ^l	✓ ^l		✓ ^l			✓ ^l						✓ ^l	
Biomarker Sample: Whole Blood: Immunophenotyping (TBNK, B cell subsets) ^m		✓ ^j		✓ ^l		✓ ^l			✓ ^l						✓ ^{k,l}	
Biomarker Sample: Interferon signature ^m	✓			✓					✓						✓ ^k	
Rx TREATMENT																
Randomization/drug assignment		✓														
Dispense study drug ⁱ		✓		✓	✓	✓	✓	✓	✓	✓	✓	✓	✓	✓		

	Screening	Baseline	Week 2	Week 4	Week 8	Week 12	Week 16	Week 20	Week 24	Week 28	Week 32	Week 36	Week 40	Week 44	Week 48/ Premature Discontinuation	30-Day Follow Up Phone Call*
Visit Window (Days)			± 3	± 7												
Dispense subject diaries		✓														
Review and copy subject dosing diary and perform drug reconciliation ⁱ			✓	✓	✓	✓	✓	✓	✓	✓	✓	✓	✓	✓	✓	

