The physician will rate global assessment of the subject's current disease activity, ranging from 0 to 3 independent of the subject's self-assessment using the visual analogue scale, which consists of a horizontal 3-inch line anchored at either end by opposite adjectives reflecting the spectrum/severity of the parameters assessed at visits specified in Section 2.1.

Swollen and Tender Joint Count Assessment

An assessment of 28 joints will be done by directed physical examination at visits specified in Section 2.1. Joint swelling will be classified as present ("1"), absent ("0"), replaced ("9"), or no assessment ("NA"). Joint tenderness will additionally be classified as present ("1"), absent ("0"), replaced ("9"), or "NA."

Any injected joints will be considered as "not assessed" ("NA") for 3 months from the time of the intra-articular injection.

If possible, the swollen joint count (SJC) and tender joint count (TJC) should be performed by an independent and blinded joint assessor who should not perform any other study-related procedures.

In order to minimize variability, the same independent joint assessor should evaluate the subject at each visit for the duration of the trial as much as possible. A back-up independent joint assessor should be identified. The independent joint assessors should be a qualified medical professional (e.g., nurse, physician's assistant, physician). Any other joint assessor must be trained and competent in performing such assessments. It is the responsibility of the investigator to ensure that all assessors are qualified and trained to perform joint assessments. If the independent assessor is not available, the preidentified back-up assessor should perform such assessments.

SLE Disease Activity Index (SLEDAI)-2K assessment

The SLEDAI-2K is a global index that evaluates disease activity over the previous 30 days and includes 24 items collecting specific manifestations in 9 organ systems: neurological, musculoskeletal, renal, mucocutaneous, general, heart, respiratory, vascular, and hematological. The SLEDAI-2K scores all active (not merely emerging) rash, alopecia, oral ulcers, and proteinuria, and collects disease aspects as present or absent. Thus, it may not reflect partial improvement.

British Isles Lupus Activity Group (BILAG) assessment 2004

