9.3 Analysis of Laboratory Data

Data collected from central and local laboratories, including additional laboratory testing due to an SAE, will be used in all analyses, except for baseline, where SAE-related laboratory assessments on or before the first dose of study drug will be excluded. The clinical laboratory tests defined in the protocol operations manual (e.g., hematology and clinical chemistry) will be summarized.

For the analysis of laboratory data, values observed up to 30 days after the last dose of study drug will be included.

Each laboratory variable will be summarized for all time points (starting with baseline) with the number of non-missing observations, mean and standard deviation, median, minimum and maximum.

For continued groups, mean change from baseline to each applicable post-baseline visit will be summarized for selected laboratory variables, with the number of observations, baseline mean, and visit mean. The change from baseline mean, standard error, and 95% confidence interval will be presented for the mean change from baseline within each treatment group and difference between treatment groups.

Shift tables will be provided for each hematology, clinical chemistry parameter. Shifts from Baseline to the following endpoints will be considered: post-Baseline value and final value. This analysis will be performed only for category of "low or normal" at Baseline which shift to 'high' and category of "high or normal" at Baseline which shift to category of 'low.'

For selected laboratory variables including hemoglobin, neutrophils, lymphocytes, platelets, leukocytes, creatinine, ALT, AST, bilirubin, CPK, a listing of all observations collected will be generated for subjects that had at least one post-baseline observation meeting pre-defined criteria for potentially clinically important values. The number and percentage of subjects in each treatment group who have at least one post-baseline observation meeting the pre-defined criteria for potentially clinically important values will be provided for each variable. The criteria for potentially clinically important laboratory values will be determined by NCI CTCAE version 4.03 of greater than Grade 3 or greater than Grade 4.

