Appendix C. Potentially Clinically Important Criteria for Safety Endpoints

Vital Sign	Category	Criteria for Potential Clinically Important Vital Signs
Systolic blood pressure	Low	Value \leq 90 mmHg and decrease \geq 20 mmHg from Baseline
	High	Value \geq 160 mmHg and increase \geq 20 mmHg from Baseline
Diastolic blood pressure	Low	Value \leq 50 mmHg and decrease \geq 10 mmHg from Baseline
	High	Value \geq 100 mmHg and increase \geq 10 mmHg from Baseline
Weight	High	> 7% increase from baseline
	Low	> 7% decrease from baseline

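### The laboratory PCI count in SAP 9.3 can mix values present at entry with new ones where no entry limit applies, and no planned by-arm table separates them

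*SAP*

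**What the plan says.** SAP 9.3 plans a count of "subjects in each treatment group who have at least one post-baseline observation meeting the pre-defined criteria for potentially clinically important values" for ten variables: hemoglobin, neutrophils, lymphocytes, platelets, leukocytes, creatinine, ALT, AST, bilirubin and CPK. One post-baseline value is enough, and the baseline value plays no part. The cut-off is set by CTCAE 4.03 grade. A listing shows every observation for each subject who qualifies.

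The shift tables in the same section are narrow: "This analysis will be performed only for category of 'low or normal' at Baseline which shift to 'high", plus the mirror case from high or normal to low. Moves from low to lower and from high to higher are not tabulated.

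For vital signs the same SAP does look at change. In Appendix C the weight criterion is more than a "7% increase from baseline" (or the matching decrease), and the blood-pressure criteria combine a level with a change.

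Three places in the protocol bear on this:
- Section 5.1, criterion 3, sets entry limits for AST, ALT, estimated GFR, neutrophils ("Absolute neutrophil count (ANC) < 1,000" excludes), platelets and hemoglobin. It sets none for lymphocytes, leukocytes, bilirubin or CPK.
- Section 6.1 makes a laboratory abnormality an AE only if it leads to discontinuation, needs treatment, is judged an AE by the investigator, or is found to "meet protocol-specific criteria (see Section 6.2 regarding toxicity management").
- Section 6.2, Table 4, acts on lymphocytes only at a confirmed Grade 4 value (below 200/mm³): "interrupt study drug dosing until lymphocyte count returns to at least Grade 2" or the baseline value.

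**The concern.** A PCI table by arm is normally read as a table of what happened on treatment. Here a subject who entered with lymphocytes already at Grade 3 and stayed there counts the same as one who fell to Grade 3 on study drug. The shift tables do not help, because a subject who is low at entry and drops further is in no shift category.

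Lymphopenia is an adverse event of special interest, so this is a variable that readers will look at. Grade 3 lymphocytes meet no Table 4 criterion. They reach the AE tables only through discontinuation, treatment or the investigator's judgment. For those values the PCI table is the systematic by-arm count. At stake is how clearly a descriptive safety table can be read; no endpoint or test is affected.

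**Working it through.** The plan gives no figure on this point to reproduce, so the check is of the text first and then of size.

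**1. Which variables are exposed.** Criterion 3 bears on six of the ten PCI variables: hemoglobin, neutrophils, platelets, ALT, AST and, through GFR, creatinine. These are largely shielded. Four have no direct limit: lymphocytes, leukocytes, bilirubin and CPK. For leukocytes, neutrophils of at least 1,000 rule out a total count below 1,000 (Grade 4 in Table 4) but not Grade 3.

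**2. Lymphocyte grades.** Table 4 gives Grade 2 as below 800 down to 500 and Grade 4 as below 200, so Grade 3 is below 500 down to 200. I assume the PCI grading uses the same limits.

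**3. Could anyone enter at that grade?** The documents do not say. Operations Manual 3.11 lists the SLEDAI-2K organ systems as "neurological, musculoskeletal, renal, mucocutaneous, general, heart, respiratory, vascular, and hematological", so low counts at entry are plausible, but no frequency is given.

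**4. How easily an entry value is counted again.** Appendix D schedules "Clinical chemistry, Hematology (CBC), Urinalysis, Urine Protein to Creatinine ratio (UPCR") at 13 post-baseline visits, 7 of them through Week 24. If each draw independently repeats the entry grade with probability q (assumed), the chance of at least one repeat in k draws is 1 − (1 − q)^k. At q = 0.3 this is 92% (k = 7) and 99% (k = 13); at q = 0.1 it is 52% and 75%.

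**5. Size.** Inputs: n = 65 per arm (SAP 2.4). Assumed: b, the share entering at PCI grade and counted again, at 0 to 5%; new-onset risk t = 5% in one arm and 15% in the other; no subject entering at PCI grade worsens further.
- PCI rate as planned = b + (1 − b)t
- Worsening rate = (1 − b)t
- The two differ by b in each arm, so the risk difference is (1 − b)(15% − 5%) under both.
- SD of the arm difference, in subjects = √{65[p₀(1 − p₀) + p₁(1 − p₁)]}

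Example at b = 5%. PCI: √{65[0.0975 × 0.9025 + 0.1925 × 0.8075]} = 3.98. Worsening: √{65[0.0475 × 0.9525 + 0.1425 × 0.8575]} = 3.30. Ratio 1.21.

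| b | PCI rates | Worsening rates | Risk difference, both (points) | SD, PCI | SD, worsening | Increase |
|---|---|---|---|---|---|---|
| 0 | 5.00% / 15.00% | 5.00% / 15.00% | 10.0 | 3.37 | 3.37 | 0% |
| 1% | 5.95% / 15.85% | 4.95% / 14.85% | 9.9 | 3.51 | 3.36 | 4% |
| 2% | 6.90% / 16.70% | 4.90% / 14.70% | 9.8 | 3.64 | 3.34 | 9% |
| 5% | 9.75% / 19.25% | 4.75% / 14.25% | 9.5 | 3.98 | 3.30 | 21% |

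As a share of 65, the added SD runs from about 0.2 percentage points (0.15/65) to 1.0 (0.68/65).

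**The case against.** The other side has a good deal to say.

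- **The plan follows the protocol.** Protocol 7.4 also describes the percentage meeting PCI criteria with no baseline condition. An absolute-grade count is not an error, and the vital-sign rule does not make it one. This stands, and is why the existing count should be kept.
- **The cut-off is worded as above Grade 3 or above Grade 4.** Read literally, Grade 3 lymphocytes are not PCI. Above Grade 4, however, leaves only Grade 5, which Protocol 6.1 reserves for death, so at-least is the likelier intent. If only Grade 4 counts, little remains, because confirmed lymphocytes below 200 and leukocytes below 1,000 meet Table 4 and so are AEs anyway.
- **Nothing shows that anyone enters at PCI grade.** True. Table 4's return to a baseline value is generic wording, used for several other variables. If b = 0 the change gains nothing.
- **Other outputs help.** The listing allows a hand count; visit summaries include the baseline minimum; shift tables catch normal to low; TEAEs by maximum grade and the lymphopenia AESI are tabulated by arm; an unblinded DMC reviews safety data. All true, but none of the planned tables counts worsening from baseline grade by arm. Mean change from baseline is also planned only for continued groups.

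A reader might also infer that chance gaps between arms in entry values are a special defect of this table. They are not: any event at the same rate, including the proposed worsening count, shows gaps of that kind. Only the added noise in the working is attributable to the rule.

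**Conclusion.** The point holds as a minor one. For variables without a direct entry limit, the by-arm PCI count can mix entry values with new or worsened ones, and only the listing separates them. The effect is a rate raised by b in each arm and an SD of the arm difference 0% to 21% larger over an assumed b of 0 to 5%. It rests on three things the documents do not settle: the value of b, the illustrative risks of 5% and 15%, and a cut-off that includes Grade 3.

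Two stronger readings should be resisted. One is that the PCI table is biased for or against a treatment. Randomization excludes directional bias, and the expected risk difference equals that of a worsening count. The other is that a safety signal is diluted because the risk ratio would fall from 3.0 to 1.97 at b = 5% (19.25/9.75). That arithmetic is right, but no ratio is planned and b is assumed. No planned test, endpoint or AESI count changes.

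**What to change.** Keep the PCI count and the listing. For the PCI variables, add to SAP 9.3, by arm:

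1. the number and percentage of subjects whose post-baseline grade meets the cut-off and is worse than their own baseline grade;
2. a table of baseline grade by worst post-baseline grade.

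The cost is a few lines of SAP text and two descriptive tables from values already collected. The downside is that subjects with no baseline value, or already at Grade 4 at entry, cannot appear as worsened. They stay visible only in the existing PCI count, which is the reason to keep it.

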Adverse events will be monitored throughout the study to identify any of special interest that may indicate a trend or risk to subjects.

Adverse Events of Special Interest

The following adverse events of special interest (AESI) will be monitored during the study:

- Serious infections
- Opportunistic infections
- Herpes zoster
- Active TB
- Malignancy (all types)
- Adjudicated GI perforations
- Adjudicated cardiovascular events (e.g, MACE)
- Anemia
- Neutropenia
- Lymphopenia
- Renal dysfunction
- Hepatic disorders
- Adjudicated embolic and thrombotic events (non-cardiac, non-CNS) including venous thromboembolic events defined as pulmonary embolism and deep vein thrombosis.

Adverse Event Severity and Relationship to Study Drug

Investigators will rate the severity of each AE according to the National Cancer Institute (NCI) Common Terminology Criteria for Adverse Events (CTCAE) version 5, which can be accessed at: https://ctep.cancer.gov/protocoldevelopment/electronic_applications/docs/ctcae_v5_quick_reference_8.5x11.pdf.

If no specific grading criteria are provided for the reported event, then the event should be as follows:

- Mild (Grade 1): asymptomatic or mild symptoms; clinical or diagnostic observations only; intervention not indicated;
- Moderate (Grade 2): minimal, local or noninvasive intervention indicated; limiting age-appropriate instrumental activities of daily living (ADL) (instrumental ADL refer to preparing meals, shopping for groceries or clothes, using the telephone, managing money, etc.);
- Severe (Grade 3 - 5):
 - Grade 3: severe or medically significant but not immediately life-threatening; hospitalization or prolongation of hospitalization indicated; disabling; limiting self-care ADL (self-care ADL refers to bathing, dressing and undressing, feeding self, using the toilet, taking medications, and not bedridden);

- Grade 4: Life-threatening consequences; urgent intervention indicated;
- Grade 5: Death related to AE.

The investigator will use the following definitions to assess the relationship of the AE to the use of study drug:

Reasonable Possibility – After consideration of factors including timing of the event, biologic plausibility, clinical judgment, and potential alternative causes, there is sufficient evidence (information) to suggest a causal relationship.

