Subjects must be discontinued from study drug for an ECG change considered clinically significant and with reasonable possibility of relationship to study drug OR a confirmed absolute Fridericia's correction formula (QTcF) value > 500 msec or confirmed increase of ≥ 60 msec from Baseline.

Management of Muscle-Related Symptoms

If a subject experiences symptoms suggestive of myositis or rhabdomyolysis, CPK and aldolase measurements should be requested and will be provided after review by the TA MD with clinical management and/or study drug interruption as deemed appropriate by the treating physician. Please refer to [Table 4](#) below for further instructions.

Management of Thrombosis Events

Subjects who develop symptoms of thrombosis should be promptly evaluated and treated appropriately. If the diagnosis of deep vein thrombosis, pulmonary embolus, or non-cardiac, non-neurologic arterial thrombosis is confirmed, the subject must be discontinued from study drug.

Management of Select Laboratory Abnormalities

For any given laboratory abnormality, the investigator should assess the subject and apply the standard of care for medical evaluation and treatment following any local guidelines. Specific toxicity management guidelines for abnormal laboratory values are described in [Table 4](#) and may require a supplemental eCRF to be completed (see Section 6.1 Complaints and Adverse Events). All abnormal laboratory tests that are considered clinically significant by the investigator will be followed to a satisfactory resolution. If a repeat test is required per [Table 4](#), the repeat testing must occur as soon as possible.

Table 4. Specific Toxicity Management Guidelines for Abnormal Laboratory Values

Laboratory Parameters	Toxicity Management Guidelines
Hemoglobin	
 • If hemoglobin < 8 g/dL interrupt study drug dosing and confirm by repeat testing with a new sample. • If hemoglobin decreases ≥ 3.0 g/dL from baseline without an alternative etiology, interrupt study drug dosing and confirm by repeat testing with new sample. • If hemoglobin decreases ≥ 3.0 g/dL from baseline and an alternative etiology is known, the subject may remain on study drug at the investigator's discretion. 
If confirmed, continue to withhold study drug until hemoglobin value returns to normal reference range or its baseline value.

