Absolute neutrophil count (ANC)	
If confirmed < 750 cells/μL by repeat testing with new sample, interrupt study drug dosing until ANC value returns to normal reference range or its baseline value. Subjects who meet this criterion should be evaluated for an alternative etiology and closely monitored for infections.
 
 • The alternative etiology should be documented appropriately in the eCRF. If restarting study drug, documentation should include reason rechallenge is expected to be safe.
Platelet count	
If confirmed < 30,000 platelets/μL by repeat testing with new sample, interrupt study drug dosing until platelet count returns to normal reference range or its baseline value.

Laboratory Parameters	Toxicity Management Guidelines

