9.2.3 Treatment-Emergent Adverse Events by SOC and/or PT

Treatment-emergent adverse events, including COVID-19 related TEAEs, will be summarized by SOC and PT; by maximum relationship to study drug as assessed by the investigator (e.g., reasonable possibility or no reasonable possibility) and SOC and PT; by maximum toxicity grade and SOC and PT; and by subject number and SOC and PT. Specific adverse events will be counted once for each subject for calculating percentages, unless stated otherwise. In addition, if the same adverse event occurs multiple times within a subject, the maximum toxicity grade and level of relationship to investigational product will be reported.

In addition, TEAEs will be summarized by PT and sorted by decreasing frequency for the total active group.

TEAEs through Week 24, through Week 48 and through Week 48 per 100 patient-years of study exposure will be presented for the AE categories defined above.

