Appendix B. Definition of Adverse Events of Special Interest

Adverse Events of Special Interest (AESI) will be identified using the following search criteria:

AESI	Type of MedDRA Query	Broad or Narrow Search	SMQ/CMQ Search Criteria
Serious Infections	CMQ		"Infections" – Subset for SAEs
Opportunistic Infection excluding Tuberculosis and Herpes Zoster	CMQ (code 80000189)		"Opportunistic Infection excluding Tuberculosis and Herpes Zoster"
Herpes Zoster	CMQ (code 80000175)		"Herpes Zoster"
Active Tuberculosis	CMQ (code 80000188)		"Active Tuberculosis"
Possible Malignancy	SMQ	Narrow	"Malignancies"
Malignancy	SMQ	Narrow	"Malignant Tumours"
Non-Melanoma Skin Cancer (NMSC)	SMQ	Narrow	"Skin Malignant Tumours" (SMQ 20000204) removing Melanoma CMQ (code 80000119)
Malignancies excluding NMSC	SMQ	Narrow	"Malignant Tumours" removing NMSC output
Adjudicated GI perforations			Based on adjudicated results (the identification of events to be adjudicated are described in the GI Perforation charter)
Adjudicated cardiovascular events: MACE* Cardiovascular Death Non-fatal Myocardial Infarction Non-fatal Stroke Undetermined/Unknown Cause of Deaths Other Cardiovascular events	Output from CAC		
Anemia	CMQ		"Non-Hemolytic and Non-Aplastic Anemias"

AESI	Type of MedDRA Query	Broad or Narrow Search	SMQ/CMQ Search Criteria
Neutropenia	CMQ		"Hematological Toxicity – Neutropenia"
Lymphopenia	CMQ		"Hematological Toxicity – Lymphopenia"
Renal dysfunction	SMQ	Narrow	"Acute Renal Failure"
Hepatic disorders	SMQ	Narrow	"Drug Related Hepatic Disorders" - Comprehensive Search SMQ
Adjudicated Thrombotic Events: VTE** Deep Vein Thrombosis Pulmonary Embolism Other Venous Thrombosis	Output from CAC		

* MACE: Major Adverse Cardiovascular Events, defined as cardiovascular death, non-fatal myocardial infarction and non-fatal stroke.

** VTE: Venous thromboembolic events, defined as deep vein thrombosis (DVT) and pulmonary embolism (PE) (fatal and non-fatal).

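### Read as written, the laboratory PCI threshold in SAP 9.3 counts Grade 4 values only: subjects whose worst value is Grade 3 drop out, and the second tier is empty

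*SAP*

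**What the plan says.** SAP 9.3 names ten laboratory variables: hemoglobin, neutrophils, lymphocytes, platelets, leukocytes, creatinine, ALT, AST, bilirubin and CPK. For each it plans two outputs. One is the number and percentage of subjects per arm with at least one post-baseline PCI value. The other is a listing of all observations for those subjects. Both depend on one threshold, "determined by NCI CTCAE version 4.03 of greater than Grade 3 or greater than Grade 4".

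No other section supplies a laboratory grade. Protocol 7.4 refers to pre-defined criteria without giving them. SAP Appendix C covers vital signs only. The interim safety list in SAP 11.2.4 and the version history in SAP 13.0 give no grade.

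The only full grade scale in the documents is in Protocol 6.1. It classes Grade 3 as severe and ends with "Grade 5: Death related to AE".

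**The concern.** The threshold uses strict inequalities where inclusive ones would be expected. A programmer who follows the text omits every subject whose worst value is Grade 3 and produces a second tier that is always empty. A programmer who does not follow it departs from the plan. The documents do not show which was done.

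No hypothesis test, efficacy endpoint or stopping rule uses this threshold. What is at stake is how the safety tables read: a count of zero or one in an arm could be taken as reassurance when it comes from the cut-off. The PCI table carries more weight for any terminated arm, because SAP 9.1 limits the mean-change analyses of laboratory data to continued groups.

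**Working it through.** The plan states no figure on this point to reproduce. The check has four steps.

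**1. Grades that qualify.** Let a laboratory value take Grades 0 to 4, with Grade 5 meaning death (Protocol 6.1).

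- As written: above 3 gives {4}; above 4 gives the empty set; either one gives {4}.
- Inclusive: 3 or higher gives {3, 4}; 4 or higher gives {4}.

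If Grade 5 is formally allowed, the second tier becomes {5}, which is still not a laboratory value.

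**2. Examples from Protocol Table 4.** For lymphocytes, Grade 2 runs from below 800 down to 500/mm³ and Grade 4 is below 200. For white cells, Grade 2 runs from below 3000 down to 2000/mm³ and Grade 4 is below 1000. The gap between them is Grade 3: lymphocytes 200 to <500 and white cells 1000 to <2000. A lymphocyte count of 350 or a white cell count of 1500 would not be flagged as written, and would be under the inclusive rule.

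**3. Variables affected.** Ten are named. SAP 9.3 counts three of them (ALT, AST, bilirubin) separately by multiples of the upper limit of normal. That leaves 10 − 3 = 7 with no other graded laboratory count in the section.

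**4. Size.** The documents give no grade rates, so g3 and g4 below are assumptions: the shares of subjects whose worst post-baseline grade is 3 or 4. The planned arm size is n = 65.

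- Omitted per arm per variable = 65 × g3: 1.3, 3.25 and 6.5 for g3 = 2%, 5% and 10%.
- Expected PCI count at g4 = 1%: 65 × 0.01 = 0.65 as written. Under the inclusive rule, 65 × (g3 + 0.01) = 1.95, 3.90 and 7.15.
- Chance that an arm shows zero: (1 − g4)^65 as written, (1 − g3 − g4)^65 under the inclusive rule.

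| g4 | As written | Inclusive, g3 = 2% | Inclusive, g3 = 5% | Inclusive, g3 = 10% |
|---|---|---|---|---|
| 0.5% | 72% | 19.3% | 2.5% | 0.07% |
| 1% | 52% | 13.8% | 1.8% | 0.05% |
| 2% | 27% | 7.0% | 0.9% | 0.02% |

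For example, at g4 = 1% and g3 = 2%: 0.99^65 = 0.520 and 0.97^65 = 0.138.

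**The case against.** The strongest reply is that this is a slip of wording. A planned tier that nobody can enter suggests that Grade 3 or greater and Grade 4 or greater were meant, and a programmer would probably query it. That is likely, but the documents do not say so, and this sentence is the only definition.

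The second reply is that Grade 3 values stay visible elsewhere. This is partly right:

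- SAP 9.3 states that "Shift tables will be provided for each hematology, clinical chemistry parameter", and by-visit minimum and maximum values are reported. The shifts use only low, normal and high, and a subject already low at baseline cannot be counted as shifting to low.
- SAP 9.2.3 tabulates adverse events "by maximum toxicity grade and SOC and PT", and Appendix B has searches for anemia, neutropenia, lymphopenia and renal dysfunction. It has none for CPK, leukocytes or platelets. All of these need an adverse event record. Protocol 6.1 says "Laboratory abnormalities and changes in vital signs are considered to be AEs only if they result in discontinuation from the study", and the same sentence adds medical intervention, protocol-specific criteria and the investigator's own judgement.
- Protocol Table 4 brings some values within those protocol-specific criteria, for example hemoglobin ("interrupt study drug dosing and confirm by repeat testing with a new sample") and platelets ("interrupt study drug dosing until platelet count returns to normal reference range or its baseline value"), as well as neutrophils and creatinine.
- The DMC reviews unblinded data quarterly (SAP 11.1).

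None of these gives a graded laboratory count by arm. Two areas are least covered. Asymptomatic CPK elevation is one: sites are blinded to CPK, so they cannot readily report a rise they do not see, although normal-to-high shifts and the maximum are still tabulated. Grade 3 lymphocyte and leukocyte values are the other: the Table 4 criteria for both start at Grade 4, and eligibility criterion 3 sets no floor for either. Sites are not blinded to these counts, so an investigator may still report such a value as an adverse event. That narrows the gap, but capture then depends on judgement.

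The third reply is that the rates are invented and leave out low ones. This stands as a limit on the numbers. At g3 = 0.5% and g4 = 1%, about 0.3 subjects per arm are omitted (65 × 0.005), and the chance of zero moves only from 52% to 37% (0.985^65). Terminated arms may also have shorter follow-up.

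**Conclusion.** The concern holds on the text. Followed literally, the rule counts Grade 4 only, its second tier is empty, and subjects whose worst value is Grade 3 are absent from the PCI counts and do not trigger the listings. The consequence is bounded: it falls on descriptive safety output, chiefly for the seven variables without a separate graded count, and most of all on CPK, lymphocytes and leukocytes.

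Three assumptions matter. The CTCAE v4.03 tables are not in the documents, so the empty second tier rests on the Protocol's general scale, which accompanies version 5. The Grade 3 bands for lymphocytes and white cells are inferred from Table 4 and assume that its grades match v4.03. The omitted counts and zero-count probabilities rest on assumed rates and show only how much the cut-off could matter. The conclusion about which grades qualify does not depend on those rates.

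**What to change.** Replace the threshold in SAP 9.3 with two inclusive tiers, Grade 3 or higher and, separately, Grade 4 or higher. If the sponsor intends Grade 4 only, the SAP should say so and delete the second tier. In either case, confirm that the programs for the Week 24 Primary Analysis and the Final Analysis use the stated thresholds.

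The cost is one SAP sentence and a check of the program thresholds. Under the inclusive rule more subjects will appear in the PCI tables and listings. No test, endpoint or clinical rule changes.
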